#### 1.3.2 Healthy lean stool donors

*Inclusion criteria:* Men or women 18–45 years old, BMI 18.5-23kg/m^2, not related to or sharing the household with any of the recipients. Donors will be matched by sex with the FMT recipients.

#### Exclusion criteria:

The following exclusion criteria are standard at the University Health Network Transplant program for all donors:

- History or symptoms suggestive of underlying gastrointestinal disease, such as:
  - Inflammatory bowel disease
  - Gastrointestinal motility disorder
  - Diverticular disease
  - Other chronic symptoms of diarrhea NYD
  - Episode of acute diarrhea in the last 3 months
  - Irritable bowel syndrome
  - Chronic constipation
- Infection or colonization with transmissible agents, including:
  - HIV-1/2
  - Hepatitis A, B and C viruses
  - HTLV-1/2
  - Syphilis
  - VRE, MRSA, Carbapenemase-producing Organisms (CPO), Extended spectrum betalactamase-producing (ESBL) organisms
  - Clostridium difficile
  - Salmonella, Shigella, Enterotoxigenic E. Coli, E.coli 0157-H7 and other Shiga-toxin producing E. Coli, Yersinia, Campylobacter, Aeromonas, Plesiomonas, and Vibrio
  - Enteric viruses (norovirus, rotavirus and adenovirus)
  - $\circ$  Ova and parasites
  - *Helicobacter pylori*

- Gonorrhea
- Chlamydia
- History of active malignancy, or any cancer within the last 5 years (excluding basal cell carcinoma of skin).
- Risk factors for prion-related disease, including: family history of Creutzfeld-Jacob Disease, corneal or dural transplant, or receipt of human-derived pituitary growth factor.
- History of high risk for recent acquisition of HIV, Hepatitis B or Hepatitis C, as determined by self-screening using a questionnaire of risk-associated behavior
- History or signs of chronic sexually transmitted infections, such as genital ulcerative diseases, anogenital herpes, anogenital warts, cancroid or syphilitic lesions.
- Immunosuppression, as determined by history or suggestive physical signs. Items on history that indicate immunosuppression include:
  - o use of any immunosuppressive medication within last 6 months, including any dose of prednisone
  - o chronic underlying condition known to produce immunosuppression (e.g. systemic lupus erythematosus, end-stage renal disease)
- Physical signs suggestive of immunosuppression include:
  - o oral thrush
  - o lesions of Kaposi sarcoma
  - o disseminated lymphadenopathy
- History or physical findings of chronic liver disease or cholestasis
- Evidence of active encephalitis or meningitis
- Evidence of active systemic viral, bacterial or fungal infection, including malaria and tuberculosis
- Receipt of live vaccine in preceding 30 days
- Receipt of blood transfusion from a country other than Canada in preceding 6 months
- History of dementia or degenerative neurological disorders of unknown etiology
- Recent bite from an animal that may have rabies within the past 6 months
- Antibiotic use in the 6 months preceding donation
- Probiotic agent use for medicinal purposes in the 3 months prior to donation
- Use of cholestyramine within 3 months of donation
- Known and current history of blood in stools
- Travel outside Canada/United States in the past 6 months
- Health care workers
- Persons who have recently been hospitalized or discharged from long term care facilitites
- Persons who regularly attened outpatient medical or surgical clinics
- Persons who have recently engaged in medical tourism
- Use of any prescription or nonprescription medications, supplements, vitamins, herbal remedies on a regular basis
- History of COVID-19 in last 3 months
- Symptoms suggestive of COVID-19 or close contact with known or suspected COVID-19 infected person or travel history of any country known to be affected by COVID-19 in last one month

Additional exclusion criteria that apply to all donors for repeat FMT and the donors in our study:

• History, family history in first degree (blood) relatives, or current screening symptoms (as determined by positive MINI, Ham-A or MADRS) of psychiatric illness (including depression, anxiety disorder, post-partum depression, bipolar disorder, schizophrenia)

- History or family history of autoimmune disease in first degree (blood) relatives
- Family history in first degree (blood) relatives of colorectal cancer
- Anaphylactic food and environmental allergies
- Overweight (BMI  $\geq 25 \text{ kg/m}^2$ ) at any time during lifetime
- Actual BMI lower than 18.5 or higher than 23 kg/m^2
- Waist circumference > 80 cm for women, > 102 cm for men
- Diabetes or "pre-diabetes", defined as HbA1c > 6% according to FMT screening protocol, or HOMA-IR more than 2.73 (129) specifically for this study
- Smoker (cigarette, marijuana, other)
- Use of recreational drugs
- Greater than 2 alcoholic beverages per day on a regular basis

# **1.4 Intervention**

Morbidly obese participants will receive one single dose of fecal filtrate prepared from feces of healthy lean pre-screened donors (allogenic FMT) or prepared from their own feces (autologous FMT) per colonoscopy. Patients will be followed for 3 months post FMT. Patients will be allocated to allogenic or autologous FMT by randomization. As diet can influence the IM composition (131, 132), all patients will receive a brief initial counselling on a healthy diet, where they will be provided with a sheet listing the most important rules for a healthy diet, a copy of Canada's food guide, and an information sheet on a low glycemic index diet from the Canadian Diabetes Association. These are standard tools that [name] is using in her clinic for patients with non-alcoholic fatty liver disease at the University Health Network.

# 1.4.1 Stool collection for FMT

Patients and donors will receive a stool collection kit including a collection bowl with a lid, an insulated bag and cooling elements. They will collect one full stool and keep it in the home refrigerator (4°C) for 24 hours (maximum 48 hours) before bringing it to the hospital in the insulated bag with the cooling elements (*see instructions*).

# 1.4.2 Preparation of fecal filtrate for FMT

Allogenic and autologous FMT will be produced the same way, using either healthy lean donor stool or the recipient's own stool, respectively.

### FMT manufacturing

FMT manufacturing will follow actual methodologies used in [name] laboratory, based on their previous randomized controlled trial (NCT01226992).

# FMT delivery

FMT by colonoscopy will be administered on one occasion using FMT derived from 150 g stool.

- Three 50 g frozen FMT, each in 30 mL conical tubes, from the same donor (i.e. a total of 150 g frozen FMT) will be thawed at 2-5°C over 24-48 hours in order to best maintain the integrity of microorganisms.
- Each thawed FMT will be diluted with sterile 0.9N NaCL to make up a total volume of 100 mL per "50g dose" and place into transport container (total volume 300 mL)
- The diluted filtrate will be transported at room temperature to the endoscopy suite in a biosafety specimen transportation bag.

- Once received by the gastroenterology team the filtrate will be administered within 9 hours throughout the colon using a colonoscope.
- Store 2 aliquots of the filtrate in 2ml vials, labelled with the same unique donor identification number, and frozen in the -80°C freezer in the event that further testing is required in the future.
- The colonoscopy procedure and post-procedure observation will otherwise follow standard medical procedures. The FMT by colonoscopy will be administered by a trained gastroenterologist.

The amount of 150 g stool suspended in 300 mL reflects the range of acceptable stool mass and volume in published literature (102). Freezing the stool up to 6 months (increasing to 12 months as soon as data from [name] lab will become available) in Normal Saline containing glycerol as a cryopreservant has been shown not to affect the efficacy against C. difficile or the viability of representative organisms (133).

Patients who are allocated to the allogenic FMT still provide a stool sample (as this is a double-blind study). The laboratory technician who is allocating the groups based on the randomization list will produce an autologous FMT only for those patients who are in this arm. The FMT products for administration will be labelled only with the study ID of the recipient, in order to keep the double-blind design. The aliquots that are kept from the lean healthy donors for future testing are labelled with the donor's study ID. Allogenic FMT will be delivered only after the corresponding donor has passed the second safety screening (same sample as the first one: stools, urine and blood).

# 1.4.3 Administration of FMT by colonoscopy

For FMT, subjects undergo standard preparation for colonoscopy (*colonoscopy preparation attached*), starting with adjustment of diet 5-7 days prior to colonoscopy and clear fluids only 2 days before the procedure. Two days before the procedure, patients have to take 2 tablets of Dulcolax at 5:00pm. The evening prior to colonoscopy, 4 L polyethylene glycol laxative solution have to be taken to complete bowel cleansing. Colonoscopy will be performed according to medical and safety standards at the University Health Network. Once received by the gastroenterology team the filtrate will be dispensed into six 60ml syringes. Then the fecal filtrate will be administered while the colonoscope is slowly removed. No FMT will be administered in the ileum, to avoid potential infection due to the bacteria from the filtrate to reach the bloodstream through the small solution of continuity due to the biopsy in the ileum. The whole amount (300ml) of filtrate will be administered in the cecum/ascending colon at an infusion rate of about 50ml/min. At the time of infusion, the patients will be in his left lateral recumbence position and will be asked to maintain a right lateral position for at least 1 hour after the procedure to facilitate as much as possible the permanence of the material infused into the proximal portions of the colon.

### 1.4.4 Rationale for dose and route of administration selected

Even though FMT is increasingly used in the treatment of *C. difficile* infection and other gastrointestinal diseases in clinical practice and research (102, 103), there are currently no standards for the collection of donor feces and preparation of the fecal filtrate. Usually, the donor specimen is homogenized and filtered and either administered directly or frozen and used later (102, 136). Gastrointestinal tubes, colonoscopy, enema, and recently even oral capsules are used to administer FMT (102). In the present trial we will freeze the filtrate before administration via colonoscopy.

We are preparing the fecal filtrate using standard methods developed at Mount Sinai Hospital, which

have been used in a previous Health Canada approved trial on FMT for *C. difficile* infection (NCT01226992, clinicaltrials.gov). The amount of filtrate to be administered was changed from 50 g feces in 500 mL saline to 150 g in 300 mL, as this stool volume is now the standard amount used in our own FMT program at Mount Sinai Hospital. Colonoscopy is a safe way to administer FMT (102). This route was selected, as it allows us to reach more proximal regions of the gut compared to enema. We decided against small intestinal infusion used by Vrieze for their metabolic syndrome study (26), as we are treating morbidly obese individuals that may have large BMI (>40 kg/m^2) and we are concerned with the higher prevalence of gastroesophageal reflux in this population (137), which may increase the risk of aspiration.

Due to the control arm receiving autologous FMT, we are using frozen fecal filtrate. Patients need to prepare for FMT colonoscopy following standard instructions with clear fluids and a laxative the day before the procedure to clean the colon (*see colonoscopy preparation instructions*). The stool for FMT has to be collected before the adjustment of diet and bowel preparation in order to maintain the original IM (stool need to be collected no later than 3 to 4 days prior to colonoscopy). The use of an autologous FMT control group is essential, as the bowel preparation and colonoscopy itself can induce changes to the IM (134, 135). Lean donor stool will be processed the same way as the autologous stool. Freezing stool by adding glycerol as a cryoprotectant has been shown to yield active FMT preparations (136, 138). Costello and colleagues (133) examined the long-term stability of frozen stools for FMT and confirmed that fecal filtrate for treatment of *C. difficile* infection could safely be stored frozen in 10% glycerol for at least 6 months without loss of clinical efficacy or viability in the six bacterial groups tested. In our study, we will store fecal filtrate for a maximum of 3 months before using it for FMT.

We will follow patients for 3 months post FMT. Vrieze et al. found improvements in IR already 6 weeks after FMT, without weight loss (26). We will extend the observation period, as 6 weeks might not have been sufficient to cause significant weight loss. In addition, we want to see, whether FMT leads to sustainable improvements in IR and IM. Patients will be approached by the MTOP Team and will be offered a 3 years follow-up post-FMT (REB# 16-5404-AE, separate consent form).

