Morbidly obese patients: Patients will be approached if they have attended the information session and signed the psychosocial study consent where they agree to be contacted for future research studies. We will be targeting specifically those patients who decide not to go ahead with the bariatric surgery at this point in time (i.e. no follow-up arranged four weeks after the orientation session). Patients interested in our study calling us on their own initiative will be screened even if not previously evaluated by the Bariatric Clinic at TWH as long as they fulfil all other requirements. After a short phone screening, the patients receive a copy of the consent form, which will be discussed over the phone by the study coordinator. Then they will come to the hospital for the screening visit, where their medical history and medications are recorded and HOMA-IR will be measured to assess eligibility. Patients will be provided with forms for food records, activity log, environmental questionnaire, and a stool collection kit. If the patient lives far or specifically request it, he can have blood works done in an outside lab and kit will be mailed home. In this case medical history and medications are recorded over the phone. Once eligibility is confirmed depending on HOMA-IR measured at screening, patients will be called back for the baseline visit. The following will be assessed: bloodwork, anthropometric measurements, appetite rating, psychological MINI interview, depression, anxiety, and quality of life questionnaires. Then, an FMT appointment will be scheduled and patients will be randomized. Patients will collect stool samples adequate for a single transplant (150gr) before they start the bowel preparation for the colonoscopy. In the week before the stool sample is collected, they will complete the questionnaires provided at baseline. When they bring their stool sample to the hospital, completed forms will be collected, anthropometric measurements will be performed. Baseline measurements will be repeated at 1 and 3 months post FMT, except for quality of life, depression and anxiety scores.. After FMT patients are required to fill-in a symptoms diary to keep track of any AE possibly occurring. In addition, during the colonoscopy performed to administer FMT, mucosal samples will be taken from the rectum, the colon, and the terminal ileum to assess the mucosa-associated microbiome. Blood and colon secretions will be collected to evaluate the baseline immune status of the subject (infections existing prior to FMT) and colon secretions will be also stored for future research.

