
### 1.6 Methods

#### 5.6.1 Stool Measurements

Sample collection and processing: Participants receive a stool collection kit, including a plastic collection/storage container, insulated bag, and cooling elements. Patients will collect one stool sample within 24 h before the study appointment (donors) or prior to the 2-day preparation for the colonoscopy (patients). Stools will be placed in the participant's home refrigerator (+4°C) immediately after defecation. Within 24 h (up to 48 h acceptable) the stool will be brought to hospital in the insulated bag with cooling elements, where the stool will be transferred into sterile sample bags and homogenized a stomacher. In the autologous FMT group and in the donors, 150 g of the stool will be processed for FMT as described above. Another stool sample will be collected within 72 hours prior to colonoscopy preparation and stored in patient's freezer. The sample will be stored in our -80°C freezer and then homogenized and separated. Two tubes containing 20 mg each will be stored for stool metabolomics. Three tubes of about 0.1 g stool will be stored for IM measurement, and the rest will be aliquoted in 10-20 mL tubes and stored for potential future analysis. All samples, except for FMT filtrate, will be stored at -80°C until analysis.

Protocol FMT, Version 10 May 2020

Intestinal microbiome (IM): DNA extraction: DNA will be extracted from samples using the PowerSoil® DNA Isolation Kit aiming for 100 mg of sample for stool and the entire sample for plaque (MO BIO Laboratories, Inc., Carlsbad, CA). The extraction protocol will be modified to include a lysozyme digestion step (incubation at 37°C for 30 minutes) (139). DNA concentration and purity will be measured using a Nanodrop Spectrophotometer (Thermo Scientific, Rockford, IL). Extracted DNA will be stored at -20°C until analysis.

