### 5.8 Randomization and blinding

# 5.8.1 Randomization list and blinding

Allocation concealment will be maintained by the lab technologist at the UHN-SHS FMT program, who will prepare the fecal filtrates for each patient but will otherwise not be involved in the conduct or analysis of the study. The allocation list will be kept in sequentially numbered envelopes with the group assignments. The group assignments will be based on a blocked randomization list (4 patients per block), created in SAS proc PLAN. The list will be created to randomize 60 patients, even though 36 are planned to be randomized. As we are including only dosed patients in the analysis, this will allow us to randomize additional patients, in case the FMT is not conducted in participants after they were randomized. The list is created by a person at the UHN, who will not be involved in conduct or analysis of the study. The technologist will have to date and sign the opened envelope.

The technologist will open the allocation on the day the patients at providing their baseline stool sample. Only if the patient is allocated to autologous FMT, a fecal filtrate from the patient's own feces is produced. On the day of the FMT, the bags with the fecal filtrate will be provided to the study team

without indication, which type of FMT is provided. Only the patient number will be on the label. Both the patient and the study team (clinical team, study coordinator, data analyst) will be blinded to group assignments.

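### The day limit for collecting the patient's FMT stool falls 1 to 4 days after the diet adjustment it is meant to precede; a minor inconsistency that could affect only autologous product

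*Combined protocol and SAP*

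**What the plan says.** Section 1.4.4 sets the rule and its reason: "The stool for FMT has to be collected before the adjustment of diet and bowel preparation in order to maintain the original IM". A bracket then puts it in days: "stool need to be collected no later than 3 to 4 days prior to colonoscopy".

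Section 1.4.3 describes the standard colonoscopy preparation as "starting with adjustment of diet 5-7 days prior to colonoscopy and clear fluids only 2 days before the procedure". Dulcolax follows two days before the procedure and polyethylene glycol the evening before.

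Two other places give the timing without mentioning diet. Section 1.5 has patients collect the transplant stool "before they start the bowel preparation for the colonoscopy". Section 5.6.1 (Stool Measurements) places collection "prior to the 2-day preparation for the colonoscopy (patients" and adds a second stool sample, for microbiome and metabolomics, taken within 72 hours before colonoscopy preparation.

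On use of the stool, the FMT delivery section says that all patients provide it, but the technician "will produce an autologous FMT only for those patients who are in this arm". Section 5.8.1 says the same: "Only if the patient is allocated to autologous FMT" is a filtrate made from the patient's own stool.

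**The concern.** The day count in section 1.4.4 reads as the working form of the rule before it, and it is the only figure in the protocol for how many days before colonoscopy the FMT stool must be collected. Set against section 1.4.3, it permits what the rule forbids: stool passed after the diet has changed. Sections 1.5 and 5.6.1 do not clearly close the gap, because neither names diet.

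The issue is the control product. Donors have no colonoscopy preparation, and stool from allogenic-arm patients is not made into product. Any product made from stool collected after the diet change would therefore sit in the autologous arm alone. Section 1.4 itself notes that diet can influence the composition of the intestinal microbiome, and section 1.4.4 calls the autologous control essential.

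**Working it through.** This is day-count arithmetic, in days before colonoscopy.

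**Inputs**
- Diet adjustment starts at d = 5, 6 or 7 (section 1.4.3).
- Latest collection is at s = 3 or 4 (section 1.4.4, bracket).
- Clear fluids start at 2 (section 1.4.3) or at 1 (section 1.4.4).

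**Does the limit precede the diet adjustment?** The limit falls d − s days after the diet starts; a negative value would mean it comes before.

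| Diet start d | Limit s = 4 | Limit s = 3 |
|---|---|---|
| 5 | 5 − 4 = 1 | 5 − 3 = 2 |
| 6 | 6 − 4 = 2 | 6 − 3 = 3 |
| 7 | 7 − 4 = 3 | 7 − 3 = 4 |

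All six values are positive. The limit is 1 to 4 days too late to enforce the rule.

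**Does it precede the clear-fluid phase?**
- From day 2: 3 − 2 = 1 and 4 − 2 = 2 days before.
- From day 1: 3 − 1 = 2 and 4 − 1 = 3 days before.

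So the limit is 1 to 3 days early for clear fluids. It fits a rule about bowel preparation, but not one about diet adjustment.

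**What limit would satisfy the rule?** Counting whole days, d + 1: 5 + 1 = 6, 6 + 1 = 7, 7 + 1 = 8. One day for everyone would be at least 8 days before colonoscopy. This is a whole-day convention: stool passed on the day the diet starts, but before it starts, would also comply. The limit would move (d + 1) − s days earlier, from 6 − 4 = 2 to 8 − 3 = 5 days.

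**The second sample in section 5.6.1.** If preparation there means the 2-day step, the 72-hour window runs from 2 + 3 = 5 to 2 days before colonoscopy, which is on or after the diet start. If preparation includes the diet adjustment, the window is 8 to 5 days before (5-day start) up to 10 to 7 days before (7-day start), and the sample precedes the change. This applies to both arms alike.

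**The case against.** The strongest reply is that nobody who complies collects late. The main clause is mandatory and the bracket is only an outer bound, so both must be met and the stricter governs. This stands: the 1 to 4 days describe the bound, not a planned collection day.

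Three other readings deserve a hearing.
- **Clear fluids.** Just before the rule, section 1.4.4 describes preparation only as "with clear fluids and a laxative the day before the procedure to clean the colon", and the limit does precede that. The reading fits poorly, because section 1.4.3 uses diet adjustment for a separate step, listed before clear fluids, and section 1.4.4 names diet in addition to bowel preparation.
- **Logistics.** Home refrigeration takes 24 hours, at most 48 (section 1.4.1), and thawing takes 24 to 48 hours (FMT delivery). Together that is 1 + 1 = 2 to 2 + 2 = 4 days, before any freezing or processing time, so 3 to 4 days might be the latest workable day. But the bracket directly follows the reason about keeping the microbiome unaltered, not anything about processing.
- **Section 1.5.** Bowel preparation there can be read as the whole preparation of section 1.4.3, diet included, and then section 1.5 is right. This stands as a possible reading. Section 1.4.4 lists the two separately and section 5.6.1 speaks of two days, so the terms need aligning.

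The patient-facing preparation and collection sheets are cited but not in the file. They may already give the right day.

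**Conclusion.** The bracket in section 1.4.4 is wrong as written, and the error is minor. Taking diet adjustment in the sense of section 1.4.3, the limit falls 1 to 4 days after the step it should precede. Staff relying on the day count, or on the 2-day wording in section 5.6.1, could collect after the diet change, and only autologous product would be affected.

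A reader might infer that control product will be made from altered stool, or that the HOMA-IR comparison is biased. The documents support neither. The main clause forbids late collection, and the diet adjustment is not described. Nothing in the plan says what a few days of it does to the product or to HOMA-IR. The statement in section 1.4 that diet can influence the microbiome is general and does not concern a short pre-colonoscopy diet. Size and direction are unknown.

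**What to change.** In section 1.4.4, replace the bracket with: *before the patient's own diet adjustment starts (5–7 days before colonoscopy)*. Use the same anchor in sections 1.5 and 5.6.1, including the baseline microbiome sample, and check that the attached patient instructions agree. A single fixed day, such as at least 8 days before colonoscopy, is optional.

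The change is to wording, but it has small practical effects. Scheduling becomes slightly less flexible. Three things tied to the stool visit move a few days earlier in both arms: the anthropometry taken when stool is brought in, the questionnaire week before collection (both section 1.5), and the opening of the allocation envelope (section 5.8.1). The last slightly lengthens the time from allocation to dosing. That matters a little, because patients who are not dosed are replaced and left out of the analysis (sections 1.3.1 and 5.7.3). Storage is no obstacle: section 1.4.4 already allows filtrate to be kept for up to 3 months.
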